## **17. ADMINISTRATIVE REQUIREMENTS**

### **17.1. Protocol Amendments**

Neither the investigator nor the sponsor will modify this protocol without a formal amendment by the sponsor. All protocol amendments must be issued by the sponsor, and signed and dated by the investigator. Protocol amendments must not be implemented without prior IEC/IRB approval, or when the relevant competent authority has raised any grounds for non-acceptance, except when necessary to eliminate immediate hazards to the patients, in which case the amendment must be promptly submitted to the IEC/IRB and relevant competent authority. Documentation of amendment approval by the investigator and IEC/IRB must be provided to the sponsor. When the change(s) involves only logistic or administrative aspects of the study, the IEC/IRB (where required) only needs to be notified.

During the course of the study, in situations where a departure from the protocol is unavoidable, the investigator or other physician in attendance will contact the appropriate sponsor representative listed in the Contact Information page(s), which will be provided as a separate document. Except in emergency situations, this contact should be made before implementing any departure from the protocol. In all cases, contact with the sponsor must be made as soon as possible to discuss the situation and agree on an appropriate course of action. The data recorded in the eCRF and source documents will reflect any departure from the protocol, and the source documents will describe this departure and the circumstances requiring it.

### **17.2. Regulatory Documentation**

#### **17.2.1. Regulatory Approval/Notification**

This protocol and any amendment(s) must be submitted to the appropriate regulatory authorities in each respective country, if applicable. A study will not be initiated until all local regulatory requirements are met.

#### **17.2.2. Required Prestudy Documentation**

The following documents must be provided to the sponsor before shipment of study drug to the study site:

- Protocol and amendment(s), if any, signed and dated by the principal investigator
- A copy of the dated and signed (or sealed, where appropriate per local regulations), written IEC/IRB approval of the protocol, amendments, ICF, any recruiting materials, and if applicable, patient compensation programs. This approval must clearly identify the specific protocol by title and number and must be signed (or sealed, where appropriate per local regulations) by the chairman or authorized designee.
- Name and address of the IEC/IRB, including a current list of the IEC/IRB members and their function, with a statement that it is organized and operates according to GCP and the applicable

laws and regulations. If accompanied by a letter of explanation, or equivalent, from the IEC/IRB, a general statement may be substituted for this list. If an investigator or a member of the study-site personnel is a member of the IEC/IRB, documentation must be obtained to state that this person did not participate in the deliberations or in the vote/opinion of the study.

- Regulatory authority approval or notification, if applicable
- Documentation of investigator qualifications (eg, curriculum vitae)
- Completed investigator financial disclosure form from the principal investigator, where required
- Signed and dated clinical trial agreement, which includes the financial agreement
- Any other documentation required by local regulations

The following documents must be provided to the sponsor before enrolment of the first patient:

- Completed investigator financial disclosure forms from all subinvestigators
- Documentation of subinvestigator qualifications (eg, curriculum vitae)
- Photocopy of the site signature log, describing delegation of roles and responsibilities at the start of the study
- Name and address of any local laboratory conducting tests for the study, and a dated copy of current laboratory normal ranges for these tests, if applicable
- Local laboratory documentation demonstrating competence and test reliability (eg, accreditation/license), if applicable

### **17.3. Patient Identification, Enrolment, and Screening Logs**

The investigator agrees to complete a patient identification and enrolment log to permit easy identification of each patient during and after the study. This document will be reviewed by the sponsor study-site contact for completeness.

The patient identification and enrolment log will be treated as confidential and will be filed by the investigator in the study file. To ensure patient confidentiality, no copy will be made. All reports and communications relating to the study will identify patients by patient identification and date of birth. In cases where the patient is not enrolled into the study, the date seen and date of birth will be used.

The investigator must also complete a patient screening log, which reports on all patients who were seen to determine eligibility for inclusion in the study.

### **17.4. Source Documentation**

At a minimum, source documents consistent in the type and level of detail with that commonly recorded at the study site as a basis for standard medical care must be available for the following: patient identification, eligibility, and study identification; study discussion and date of signed informed consent; dates of visits; results of safety and efficacy parameters as required by the

protocol; record of all AEs and follow-up of AEs; concomitant medication; drug receipt/dispensing/return records; study drug administration information; and date of study completion and reason for early discontinuation of study drug or withdrawal from the study, if applicable.

The author of an entry in the source documents should be identifiable.

Specific details required as source data for the study and source data collection methods will be reviewed with the investigator before the study and will be described in the monitoring guidelines (or other equivalent document).

The following data will be recorded directly into the eCRF and will be considered source data:

- Race
- History of smoking (all nicotine use, eg, cigarettes or the equivalent of e-cigarettes, cigars, chewing tobacco, patch, gum), alcohol intake
- Vital Signs (blood pressure, heart rate, respiratory rate and temperature)
- Height and weight
- Details of physical examination
- The minimum source documentation requirements for Section 4.1, Inclusion Criteria and Section 4.2, Exclusion Criteria that specify a need for documented medical history are as follows:
  - Referral letter from treating physician or
  - Complete history of medical notes at the site
  - Discharge summaries

Inclusion and exclusion criteria not requiring documented medical history must be verified at a minimum by patient interview or other protocol required assessment (eg, physical examination, laboratory assessment) and documented in the source documents.

An electronic source system may be utilized, which contains data traditionally maintained in a hospital or clinic record to document medical care (eg, electronic source documents) as well as the clinical study-specific data fields as determined by the protocol. This data is electronically extracted for use by the sponsor. If the electronic source system is utilized, references made to the eCRF in the protocol include the electronic source system but information collected through the electronic source system may not be limited to that found in the eCRF. Data in this system may be considered source documentation.

## 17.5. Case Report Form Completion

Case report forms will be prepared and provided by the sponsor for each patient in electronic format. All eCRF entries, corrections, and alterations must be made by the investigator or authorized study-site personnel. The investigator must verify that all data entries in the eCRF are accurate and correct.

The study data will be transcribed by study-site personnel from the source documents onto an eCRF, if applicable. Study-specific data will be transmitted in a secure manner to the sponsor.

The eCRF must be completed as soon as possible after a patient visit and the forms should be available for review at the next scheduled monitoring visit.

All subjective measurements (eg, pain scale information or other questionnaires) will be completed by the same individual who made the initial baseline determinations whenever possible.

If necessary, queries will be generated in the eDC tool. If corrections to an eCRF are needed after the initial entry into the eCRF, this can be done in either of the following ways:

- Investigator and study-site personnel can make corrections in the eDC tool at their own initiative or as a response to an auto query (generated by the eDC tool).
- Sponsor or sponsor delegate can generate a query for resolution by the investigator and study-site personnel.

### **17.6. Data Quality Assurance/Quality Control**

Steps to be taken to ensure the accuracy and reliability of data include the selection of qualified investigators and appropriate study sites, review of protocol procedures with the investigator and study-site personnel before the study, and periodic monitoring visits by the sponsor. Written instructions will be provided for collection, handling, storage, and shipment of samples.

The sponsor will review eCRF for accuracy and completeness during on-site monitoring visits and after transmission to the sponsor; any discrepancies will be resolved with the investigator or designee, as appropriate. After upload of the data into the study database they will be verified for accuracy and consistency with the data sources.

### **17.7. Record Retention**

In compliance with the ICH/GCP guidelines, the investigator/institution will maintain all eCRF and all source documents that support the data collected from each patient, as well as all study documents as specified in ICH/GCP Section 8, Essential Documents for the Conduct of a Clinical Trial, and all study documents as specified by the applicable regulatory requirement(s). The investigator/institution will take measures to prevent accidental or premature destruction of these documents.

Essential documents must be retained until at least 2 years after the last approval of a marketing application in an ICH region and until there are no pending or contemplated marketing applications in an ICH region or until at least 2 years have elapsed since the formal discontinuation of clinical development of the investigational product. These documents will be retained for a longer period if required by the applicable regulatory requirements or by an agreement with the sponsor. It is the responsibility of the sponsor to inform the investigator/institution as to when these documents no longer need to be retained.

If the responsible investigator retires, relocates, or for other reasons withdraws from the responsibility of keeping the study records, custody must be transferred to a person who will accept the responsibility. The sponsor must be notified in writing of the name and address of the new custodian. Under no circumstance shall the investigator relocate or dispose of any study documents before having obtained written approval from the sponsor.

If it becomes necessary for the sponsor or the appropriate regulatory authority to review any documentation relating to this study, the investigator/institution must permit access to such reports.

## **17.8. Monitoring**

The sponsor will perform on-site monitoring visits as frequently as necessary. The monitor will record dates of the visits in a study site visit log that will be kept at the study site. The first post-initiation visit will be made as soon as possible after enrolment has begun. At these visits, the monitor will compare the data entered into the eCRF with the source documents (eg, hospital/clinic/physician's office medical records). The nature and location of all source documents will be identified to ensure that all sources of original data required to complete the eCRF are known to the sponsor and study-site personnel and are accessible for verification by the sponsor study-site contact. If electronic records are maintained at the study site, the method of verification must be discussed with the study-site personnel.

Direct access to source documents (medical records) must be allowed for the purpose of verifying that the recorded data are consistent with the original source data. Findings from this review will be discussed with the study-site personnel. The sponsor expects that, during monitoring visits, the relevant study-site personnel will be available, the source documents will be accessible, and a suitable environment will be provided for review of study-related documents. The monitor will meet with the investigator on a regular basis during the study to provide feedback on the study conduct.

## **17.9. Study Completion/Termination**

### **17.9.1. Study Completion/End of Study**

The study is considered completed with the last visit of the last patient participating in the study. The final data from the investigational site will be sent to the sponsor (or designee) after completion of the final patient visit at that site, in the time frame specified in the Clinical Trial Agreement.

### **17.9.2. Study Termination**

The sponsor reserves the right to close the study site or terminate the study at any time for any reason at the sole discretion of the sponsor. Study sites will be closed upon study completion. A study site is considered closed when all required documents and study supplies have been collected and a study-site closure visit has been performed.

The investigator may initiate study-site closure at any time, provided there is reasonable cause and sufficient notice is given in advance of the intended termination.

Reasons for the early closure of a study site by the sponsor or investigator may include but are not limited to:

- Failure of the investigator to comply with the protocol, the requirements of the IEC/IRB or local health authorities, the sponsor's procedures, or GCP guidelines
- Inadequate recruitment of patients by the investigator

### **17.10. On-Site Audits**

Representatives of the sponsor's clinical quality assurance department may visit the study site at any time during or after completion of the study to conduct an audit of the study in compliance with regulatory guidelines and company policy. These audits will require access to all study records, including source documents, for inspection. Patient privacy must, however, be respected. The investigator and study-site personnel are responsible for being present and available for consultation during routinely scheduled study-site audit visits conducted by the sponsor or its designees.

Similar auditing procedures may also be conducted by agents of any regulatory body, either as part of a national GCP compliance program or to review the results of this study in support of a regulatory submission. The investigator should immediately notify the sponsor if he or she has been contacted by a regulatory agency concerning an upcoming inspection.

### **17.11. Use of Information and Publication**

All information, including but not limited to information regarding golimumab or the sponsor's operations (eg, patent application, formulas, manufacturing processes, basic scientific data, prior clinical data, formulation information) supplied by the sponsor to the investigator and not previously published, and any data, including research data, generated as a result of this study, are considered confidential and remain the sole property of the sponsor. The investigator agrees to maintain this information in confidence and use this information only to accomplish this study, and will not use it for other purposes without the sponsor's prior written consent.

The investigator understands that the information developed in the study will be used by the sponsor in connection with the continued development of golimumab, and thus may be disclosed as required to other clinical investigators or regulatory agencies. To permit the information derived from the clinical studies to be used, the investigator is obligated to provide the sponsor with all data obtained in the study.

The results of the study will be reported in a Clinical Study Report generated by the sponsor and will contain data from all study sites that participated in the study as per protocol. Recruitment performance or specific expertise related to the nature and the key assessment parameters of the study will be used to determine a coordinating investigator. Study patient identifiers will not be used in publication of results. Any work created in connection with performance of the study and contained in the data that can benefit from copyright protection (except any publication by the investigator as provided for below) shall be the property of the sponsor as author and owner of copyright in such work.

Consistent with Good Publication Practices and International Committee of Medical Journal Editors guidelines, the sponsor shall have the right to publish such primary (multicentre) data and information without approval from the investigator. The investigator has the right to publish study

site-specific data after the primary data are published. If an investigator wishes to publish information from the study, a copy of the manuscript must be provided to the sponsor for review at least 60 days before submission for publication or presentation. Expedited reviews will be arranged for abstracts, poster presentations, or other materials. If requested by the sponsor in writing, the investigator will withhold such publication for up to an additional 60 days to allow for filing of a patent application. In the event that issues arise regarding scientific integrity or regulatory compliance, the sponsor will review these issues with the investigator. The sponsor will not mandate modifications to scientific content and does not have the right to suppress information. For multicentre study designs and substudy approaches, secondary results generally should not be published before the primary endpoints of a study have been published. Similarly, investigators will recognize the integrity of a multicentre study by not submitting for publication data derived from the individual study site until the combined results from the completed study have been submitted for publication, within 12 months of the availability of the final data (tables, listings, graphs), or the sponsor confirms there will be no multicentre study publication. Authorship of publications resulting from this study will be based on the guidelines on authorship, such as those described in the Uniform Requirements for Manuscripts Submitted to Biomedical Journals, which state that the named authors must have made a significant contribution to the design of the study or analysis and interpretation of the data, provided critical review of the paper, and given final approval of the final version.

### **Registration of Clinical Studies and Disclosure of Results**

The sponsor will register and disclose the existence of and the results of clinical studies as required by law.

27. Kumar R, Sharma A and Dogra S. Prevalence and clinical patterns of psoriatic arthritis in Indian patients with psoriasis. *Indian Journal of Dermatology, Venereology, and Leprology* 2014;Vol 80-Issue 1.

**APPENDIX A: EVALUATION OF ANKYLOSING SPONDYLITIS****Modified New York criteria for classification of ankylosing spondylitis\***

| Criteria               | Description  |
|------------------------|--|
| Clinical criteria      | 
(a) Low back pain and stiffness for more than 3 months which improves with exercise, but is not relieved by rest
 
(b) Limitation of motion of the lumbar spine in both the sagittal and frontal planes
 
(c) Limitation of chest expansion relative to normal values correlated for age and sex
  |
| Radiological criterion | 
Sacroiliitis grade <math>\geq 2</math> bilaterally or grade 3-4 unilaterally
 
 
– Grade 0 = normal
 
– Grade 1 = suspicious
 
– Grade 2 = sclerosis, some erosions
 
– Grade 3 = severe erosions, widening of the joint space, some ankylosis
 
– Grade 4 = complete ankylosis
 
 |

Definite AS is present if the radiological criterion is associated with at least 1 clinical criterion

The ASAS 20 is defined as achieving:

- An improvement from baseline of  $>20\%$  and  $>1$  unit in at least 3 of the 4 ASAS domains on a scale of 0 to 10 units, and
- No worsening from baseline of  $>20\%$  and  $>1$  unit in the remaining ASAS domain on a scale of 0 to 10 units.

The four ASAS domains are the following:

1. Patient Global Assessment of Disease (0 to 10 unit Numerical Rating Scale [NRS]);
2. Total Back Pain NRS;
3. Function Bath Ankylosing Spondylitis Functional Index (BASFI) score NRS;
4. Inflammation (mean of Bath Ankylosing Spondylitis Disease Activity Index [BASDAI] NRS Question #5 and #6 for morning stiffness).

**APPENDIX B: PATIENT GLOBAL ASSESSMENT (PGA) - NRS:**

The Patient Global Assessment of Disease Activity is the patient's assessment of how active their spondylitis was on average during the last week. The BAS-G consists of two questions which ask patients to indicate, the effect the disease has had on their well-being over the last week and last 6 months. The patient will be asked to mark the box with an X on a 0 to 10 unit NRS on which the left-hand box of 0 represents "none," and the right-hand box represents "very severe".

Please read the question below and circle the box you feel is most appropriate to describe the effect your disease has had on your well being over the last week. Please only circle one box for each question. There is no wrong answer.

1. Please use the scale below to indicate the effect your disease has had on your well being over the last week.

Score out of 10

None  0  1  2  3  4  5  6  7  8  9  10 Very severe

2. Please use the scale below to indicate the effect your disease has had on your well being over the last six months.

None  0  1  2  3  4  5  6  7  8  9  10 Very severe

For clinician use only

BAS-G Score

Add scores and divide by 2. This is the BAS-G score. The higher the BAS-G score, the more severe the effect of AS on the patient's life.

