## **9. STUDY EVALUATIONS**

### **9.1. Study Procedures**

#### **9.1.1. Overview**

The TIME AND EVENTS SCHEDULE summarizes the frequency and timing of efficacy, and safety measurements applicable to this study.

Written informed consent will be obtained from all patients by the principal investigator or his/her designee prior to the performance of any protocol-specific procedure. Additional serum or urine pregnancy tests may be performed, as determined necessary by the investigator or required by local regulation, to establish the absence of pregnancy at any time during the patient's participation in the study.

Once patient is considered eligible to be enrolled in the study, patient will receive golimumab treatment for a period of 24 weeks (6 months), which will be provided free of cost. During the study period, safety data will be collected at 4-week intervals until 24 weeks and efficacy data will be collected at Week 0, Week 4, Week 14 and Week 24. Study visits through and including Week 32 may occur at the week indicated with an allowed window period of  $\pm 4$  days. If the recommended acceptable window cannot be observed, the sponsor must be contacted before scheduling a visit and a deviation in process must be noted in study documents.

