### 9.3. Efficacy Evaluations for Ankylosing Spondylitis

The ASAS Response Criteria (ASAS 20) is defined as:

- An improvement from baseline of >20% and >1 unit in at least 3 of the 4 ASAS domains on a scale of 0 to 10 units, and
- No worsening from baseline of >20% and >1 unit in the remaining ASAS domain on a scale of 0 to 10 units

The four ASAS domains are the following:

1. PGA of Disease (0 to 10 unit NRS): It is the patient's assessment of how active their spondylitis was on average during the last week and last six months. The patient will be asked to mark the box with an X on a 0 to 10 unit NRS on which the left-hand box (0) represents "not active," and the right-hand box (10) represents "very active". (Appendix B)
2. Total and Night Spinal Pain (NRS): Pain assessment represented by the average of total and nocturnal pain scores, both are assessed by two questions rated on a 0 to 10 NRS, where 0=no pain and 10=most severe pain. Total spine pain is assessed by 'How much pain in your spine due to spondyloarthritis do you have?', and nocturnal spine pain: 'How much pain in your spine due to spondyloarthritis do you have at night? (Appendix C)
3. BASFI: The BASFI is a composite score based on a patient self-administered survey of 10 questions using a 0 to 10 unit NRS that assesses a patient's degree of mobility and functional ability. The questionnaire consists of eight questions regarding function in AS and the two last questions reflecting the patient's ability to cope with everyday life. The patient will be asked to mark the box with an X on a 0 to 10 unit NRS for each of the 10 questions, on which the

left-hand box (0) represents “easy,” and the right-hand box (10) represents “impossible.” The resulting 0 to 100 score is divided by 10 to give a final 0 to 10 BASFI score. A higher BASFI score correlates to reduced functional ability. (Appendix D)

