4.1.1. Definition of Endpoints

The ASAS Response Criteria (ASAS 20) is defined as:

- An improvement from baseline of >20% and >1 unit in at least 3 of the 4 ASAS domains on a scale of 0 to 10 units, and
- No worsening from baseline of >20% and >1 unit in the remaining ASAS domain on a scale of 0 to 10 units

The four ASAS domains are the following:

- a) **Patient Global Assessment of Disease (0 to 10 unit NRS):** Patient's assessment of how active their spondylitis was on average during the last week and last six months. The patient will be asked to mark the box with an X on a 0 to 10 unit NRS (Numerical Rating Scale) on which the left-hand box (0) represents '*not active*' and the right-hand box (10) represents '*very active*'.
- b) **Total and Night Spinal Pain (NRS):** Pain assessment represented by the average of total and nocturnal pain scores, both are assessed by two questions rated on a 0 to 10 NRS, where 0='no pain' and 10='most severe pain'. Total spine pain is assessed by '*How much pain in your spine due to spondyloarthritis do you have?*', and nocturnal spine pain by '*How much pain in your spine due to spondyloarthritis do you have at night?*'
- c) **Bath AS Functional Index (BASFI):** A composite score based on a patient self-administered survey of 10 questions using a 0 to 10 unit NRS that assesses a patient's degree of mobility and functional ability. The questionnaire consists of eight questions regarding function in AS and the two last questions reflecting the patient's ability to cope with everyday life. The patient will be asked to mark the box with an X on a 0 to 10 unit NRS for each of the 10 questions, on which the left-hand box (0) represents '*easy*' and the right-hand box (10) represents '*impossible*'. The resulting 0 to 100 score is divided by 10 to give a final 0 to 10 BASFI score. A higher BASFI score correlates to reduced functional ability.
- d) **Bath AS Disease Activity Index (BASDAI):** A composite score based on a patient self-administered survey of six questions using a 0 to 10 unit NRS that assesses the patient's five major symptoms of AS: 1) *fatigue*; 2) *spinal pain*; 3) *peripheral joint pain/swelling*; 4) *areas of localized tenderness*; 5) *morning stiffness severity upon wakening*; 6) *morning stiffness duration upon wakening*. The patient will be asked to mark the box with an X on a 0 to 10 unit NRS for each of the 6 questions. To give each of the five symptoms equal

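### The plan does not settle which patient global score enters ASAS20; if it is the two-item mean, a six-month recall item attenuates that domain more at Week 14 than at Week 24

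*Protocol*

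**What the plan says.** Protocol 9.3 describes the PGA domain of ASAS20 as the patient's "assessment of how active their spondylitis was on average during the last week and last six months" and refers to Appendix B. SAP 4.1.1(a) has the same content: "how active their spondylitis was on average during the last week and last six months". Neither section says how the two periods become one score, although both give an explicit averaging rule for total and night spinal pain.

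Appendix B is not consistent with itself. Its opening sentence limits the PGA to "how active their spondylitis was on average during the last week". The form then has two items, one for the last week and one that reads "Please use the scale below to indicate the effect your disease has had on your well being over the last six months". The clinician's instruction is "Add scores and divide by 2. This is the BAS-G score". The SAP never mentions BAS-G. Appendix A lists the PGA only as a 0 to 10 scale, with no recall period.

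The construct and anchors differ as well. Protocol 9.3 and the SAP describe how active the disease is, from not active to very active. The form asks about the effect on well-being, from none to very severe.

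The other three domains look back one week: spinal pain (Appendix C), BASFI (Appendix D) and BASDAI (Appendix E).

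**The concern.** Two programmers could derive different ASAS20 results from the same data, one using the last-week item and the other the mean, and each could cite the documents.

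The choice affects the two endpoint visits unequally. At Week 14 a six-month look-back still includes a large stretch before the first dose; at Week 24 it includes little or none. A patient whose condition is identical at both visits could therefore show a smaller PGA improvement at Week 14. Both visits are efficacy endpoints, and Week 24 serves the sustained-response objective. SAP 4.1.2 also summarises each domain score at every analysis visit, where the three-of-four rule gives no protection.

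**Working it through.** The documents give no figure on this point, so there is nothing to reproduce. The check asks what follows if the two-item mean is the score analysed.

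**Inputs from the documents.** Equal weight on the two items (Appendix B). Visits at Weeks 14 and 24 (Days 98 and 168). Six months taken as R = 26 weeks, or as R = 24 weeks because Protocol 9.1.1 equates 24 weeks with 6 months. ASAS20 requires improvement above 20% and above 1 unit in at least three of four domains. 50 AS patients.

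**Assumptions, not in the documents.** The six-month answer is a time average, both items have the same baseline, and the effect is immediate and stable.

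**Formulas**, with w weeks on drug:
- Pre-dose share of the six-month item = (R − w)/R; as a share of the averaged domain, half of that.
- Share of the last-week change kept by the mean = (1 + w/R)/2 = k.
- Last-week improvement needed to pass = 20%/k and 1/k units.

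| | Week 14, R = 26 | Week 24, R = 26 | Week 14, R = 24 | Week 24, R = 24 |
|---|---|---|---|---|
| Pre-dose share of item | 12/26 = 46.2% | 2/26 = 7.7% | 10/24 = 41.7% | 0% |
| Pre-dose share of domain | 23.1% | 3.8% | 20.8% | 0% |
| Change kept (k) | 76.9% | 96.2% | 79.2% | 100% |
| Needed to pass 20% | 26.0% | 20.8% | 25.3% | 20.0% |
| Needed to pass 1 unit | 1.30 | 1.04 | 1.26 | 1.00 |

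**Domain summaries.** Take an illustrative constant improvement of 2.5 units and R = 26. The mean shows 2.5 × 0.769 = 1.92 units at Week 14 and 2.5 × 0.962 = 2.40 at Week 24. That is an apparent gain of about 0.5 units with no real change.

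**Visit window and carry-forward** (R = 26 weeks = 182 days). SAP Table 2 accepts Days 64 to 133 as Week 14. The pre-dose share of the item then runs from (182 − 63)/182 = 65% to (182 − 132)/182 = 27%. A Week 4 PGA carried forward to Week 14 would keep only (1 + 4/26)/2 = 57.7% of the change.

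**Effect on ASAS20.** Four correlated domains were simulated under the three-of-four and no-worsening rules, with the same true response at both visits. Assumed ranges: baseline mean 6.5 (SD 1.5), mean improvement 20% to 50% (SD 30% to 40%), correlation between domains 0.5 to 0.85, R = 26.
- Week 14, last-week item alone minus two-item mean: 0.6 to 1.0 points with whole-number PGA items, as on the form; 1.3 to 2.4 points with unrounded scores.
- Week 24, same contrast: 0 to 0.4 points.
- Example (mean 30%, SD 30%, correlation 0.5, unrounded): 54.2% with the last-week item; with the mean, 51.8% at Week 14 and 53.9% at Week 24.
- One run with onset delayed by four weeks (mean 35%, SD 35%, correlation 0.7, whole-number items): 59.2% against 58.2% at Week 14.

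**Yardstick.** The 95% half-width is 1.96 × √(p(1 − p)/50): 13.9 points at p = 0.5 and 12.7 at p = 0.7. A shift of 0.6 to 2.4 points is 0.3 to 1.2 patients out of 50.

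**The case against.** A reader might infer that nearly half of the Week 14 patient global describes life before treatment. It does not: 46% belongs to one item with half weight, so about 23% of one domain out of four. Under the three-of-four rule the PGA alone cannot prevent a response.

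A reader might also infer that Week 14 response is understated and that any later gain is an artefact. The documents do not establish this, for four reasons:
- Neither document states that the BAS-G mean is the ASAS20 input.
- The effect depends on how patients recall. Weighting recent weeks more heavily would shrink it, slower onset would enlarge it, and unequal baseline items would change its size.
- The six-month item also dampens worsening, which makes the no-worsening condition easier to meet.
- No comparison of Week 14 with Week 24 is planned. The endpoints are separate proportions, there is no hypothesis test, and efficacy is secondary to safety.

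These points stand and limit the finding. They do not remove it. Protocol 9.3 sends the reader to Appendix B, where the mean is the only scoring rule, so the mean is the natural reading. The attenuation would be systematic, and a wide interval does not correct it.

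A last objection concerns the remedy. Protocol 9.3 and the SAP agree on both recall periods, and narrowing the definition late in an open-label study, in a direction expected to raise Week 14 response, invites criticism. That is a fair reason to report both versions whichever is primary. It is not a reason to leave the score undefined.

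**Conclusion.** The PGA input to ASAS20 is inconsistently specified; that follows from the text alone. The consequence is conditional. If the two-item mean is used, and under time-averaged recall, equal baseline items and an immediate stable effect, the domain keeps about 77% of the change at Week 14 and 96% at Week 24 (79% and 100% with six months taken as 24 weeks). Week 14 ASAS20 may then be lower by roughly 0.6 to 2.4 points. That range rests on simulation inputs that are not in the documents, and it is small beside a half-width of 13 to 14 points. The clearer effect is on the PGA domain summaries, which would appear to improve between the two visits without real change. The point merits a wording correction and a sensitivity analysis; it does not call the ASAS20 endpoint as a whole into question.

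**What to change.** In SAP 4.1.1(a) and Protocol 9.3, state that the ASAS20 PGA domain is item 1 of the Appendix B form (last week, 0 to 10). This agrees with Appendix B's opening description and with the recall period of the other domains. Reconcile construct and anchors so that the definition describes the question patients actually answer. Report ASAS20 with the two-item BAS-G mean as a sensitivity analysis at both visits. If the sponsor prefers to keep the mean as primary, say so explicitly and run item 1 alone as the sensitivity analysis. Record when the choice was made and whether ASAS20 results had been seen.

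The cost is a few lines of text and one repeated table. Both items are already collected. The downside is that a single item is slightly noisier than a mean of two.
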